4.1.1.2 Treatment Phase

All treatment applications will be performed by an unblinded staff at the site. The unblinded staff will not be responsible for any pain or tenderness assessments. The correct location for application of the gel will be marked with a water-resistant pen to ensure the gel is applied at the same site for each application during the entire study. The topical investigational medicinal product (IMP) will be gently applied without any massaging.

At site visits on Days 1, 2, 3, 4 and 6, algometric and pain on movement (POM) VAS assessments will be performed. Compliance will be evaluated by the investigator/designee. The investigator and patient will give a global assessment of the treatment efficacy and local tolerability using a 5-point Likert scale.

Patients will use a patient diary to record adverse events, concomitant/rescue medication use on Days 1, 2, 3, 4, 5 and 6.

The algometry/tenderness will be measured such that the greater the algometry value (N/cm²), the greater the pressure required to produce the first tenderness reaction. Therefore, greater algometry values indicate less pain at the site of interest.

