8.2 Efficacy Assessments

8.2.1 Assessment of Pain on Movement

Pain on Movement will be assessed using a 100 mm visual analogue scale at baseline and at each subsequent study visit.

Place a line on the 'Scale' that best characterizes how your injured extremity feels when it's moved *now*.

No Pain | Severe Pain

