8.2.2 Algometry

Algometry will be performed at baseline and at each study visit. Algometric measurements will be performed using a calibrated caliper with digital pressure recording). Increases in pressure during measurement will be kept constant at $10 \text{ N/cm}^2/\text{s}$. The site of measurement will be marked with a water resistant marker, and measurements will be repeated at the same site. The measurements will be performed in such a way that the patient and the investigator cannot read the actual pressure exerted (covered display). The device stores the last exerted pressure,

which is then recorded on the case report form. A tenderness reaction is defined as the pressure that, under the above conditions, produced a painful sensation.

Additional information related to the algometry procedures will be detailed in a separate document.

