5.1.2 Other efficacy variables

Other efficacy variables are:

- VAS POM over the initial 12-hours (VAS AUC₀₋₁₂), 24-hours (VAS AUC₀₋₂₄), 36-hours (VAS AUC₀₋₃₆), 48-hours (VAS AUC₀₋₄₈), 60-hours (VAS AUC₀₋₆₀), 72-hours (VAS AUC₀₋₇₂), and 120 hours (VAS AUC₀₋₁₂₀);
- Change of VAS POM at hours 12, 24, 36, 48, 60, 72 and 120 from baseline (BL);
- VAS POM over the initial 72-hours (VAS AUC₀₋₇₂) in the subgroups “sprain/strain” and “contusion”.
- Change of Algometric Tenderness (N/cm²) at hours 12, 24, 36, 48, 60, 72, and 120 from baseline;
- Algometric Tenderness (N/cm²) over the initial 12-hours (N/cm² AUC₀₋₁₂), 24- hours (N/cm² AUC₀₋₂₄), 36-hours (N/cm² AUC₀₋₃₆), 48-hours (N/cm² AUC₀₋₄₈) 60-hours (N/cm² AUC₀₋₆₀) and 120 hours (N/cm² AUC₀₋₁₂₀);
- Ratio of algometry injured/contralateral sites over 72 hours and 120 hours (N/cm² Ratio AUC₀₋₇₂ and N/cm² Ratio AUC₀₋₁₂₀);
- Algometry over the initial 72-hours (N/cm² AUC₀₋₇₂) in the subgroups “sprain/strain” and “contusion”.
- Percent of subjects with no (zero) VAS POM at 120 hours;
- Global assessment of treatment efficacy at 24 hours, 48 hours, 72 hours, and 120 hours by patients using a 5-point scale (0=none, 1=poor, 2=fair, 3=good, 4=excellent);
- Global assessment of treatment efficacy at 72 hours in the subgroups “sprain/strain” and “contusion”.
- Change of VAS PAR at hours 12, 24, 36, 48, 60, 72 and 120 from baseline (BL).

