5.4 Derived variables

Area under the curves, calculated using the trapezoidal rule [1], will be determined for POM VAS pain scores and algometric tenderness. For quantitative variables the absolute changes from baseline (Visit 1) will also be determined.

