14.8 Missing data

- If assessments at any visit for Visits 2 (12 h) through Visit 10 (108 h) are missing, they will be imputed as the average of the preceding and the following assessments. Fractional values will be rounded down (including ordered categorical assessments). If assessment at Visit 11 is missing, the last observation will be carried forward.
- If a patient terminates prematurely,
 - all subsequent visits will be imputed by carrying the last non-missing observation forward,
 - for an adverse event suspected to be study-drug-related, then all subsequent visits will be imputed by carrying the baseline observation forward,
 - for lack of efficacy, all subsequent assessments will be imputed as the worst of all documented assessments,
 - for lack of efficacy or for an adverse event suspected to be study-drug-related and does not complete the global assessment of treatment satisfaction, it will be assigned the worst possible score,
 - If a patient discontinues for any other reason, missing global assessments at Visit 11 will be imputed by the worst possible outcome.
- If a patient assesses efficacy at the site < 6 hours after using rescue medication, imputation will be discussed in the Blind Review Meeting, with consideration given to the frequency of this issue in the database and the elapsed time between rescue and assessment of efficacy.
- If a patient assesses spontaneous pain intensity and spontaneous pain relief at the time of rescue taken because of blunt trauma pain, any assessment conducted in the following 6 h will be replaced by the corresponding assessment done at the time of rescue.
- If the patient provides no post-baseline efficacy data, imputation will be considered in the Blind Review Meeting.

A Blind Review Meeting will take place before unblinding the randomization code. Handling of missing values/censoring/discontinuation, if necessary, will be provided and discussed in the Blind Review Meeting. Additional data handling rules will be specified in the BRM minutes to cover issues not anticipated in the above stipulations.

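### SAP 14.8 rounds imputed continuous values down, which worsens algometry but improves POM, and gives a wholly missed 72-h value equal weights at 60 h and 120 h (minor)

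*SAP*

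**What the plan says.** SAP 14.8 covers missed assessments at Visits 2 (12 h) to 10 (108 h): "they will be imputed as the average of the preceding and the following assessments. Fractional values will be rounded down (including ordered categorical assessments". There are no time weights and no stated precision. The bracketed words show that rounding is not limited to ordinal scores. A missed Visit 11 is carried forward, and premature termination has its own rules.

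SAP 5.4 sets the AUC method: "Area under the curves, calculated using the trapezoidal rule [1], will be determined for POM VAS pain scores and algometric tenderness".

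The measurement times are unequally spaced. SAP 5.1.2 lists "Change of VAS POM at hours 12, 24, 36, 48, 60, 72 and 120 from baseline", with the same hours for algometry. Protocol 4.1.1.2 states: "At site visits on Days 1, 2, 3, 4 and 6, algometric and pain on movement (POM) VAS assessments will be performed". The visit lists for Visits 8 to 10 (Protocol 8.1.9 to 8.1.11) and SAP Table 5-1 show neither measure at 84, 96 or 108 h.

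The two scales run in opposite directions. For algometry, "greater algometry values indicate less pain at the site of interest" (Protocol 4.1.1.2). The POM scale runs from no pain to severe pain (Protocol 8.2.1).

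**The concern.** Two features of the rule do not suit continuous measures.

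- **Rounding.** Rounding down is a one-sided error. It lowers imputed algometry (worse) and imputed POM (better), so it is not consistently conservative. Its relative size grows as values fall. Entry criteria 3 and 5 (Protocol 5.1) allow a contralateral value as low as 2.5 N/cm², with the injured site at half of that or less. A POM of 1 mm at 60 h and 0 at 120 h gives 0.5 at 72 h, rounded to 0. That brings the event forward from 120 h to 72 h in the Kaplan-Meier plot of zero POM (SAP 14.4.3).
- **Weighting.** A single missed visit at 12 to 60 h has neighbours 12 h away on each side, so the plain mean is linear interpolation. At 72 h the same sentence does something different, because the next measurement is at 120 h. The 72-h value closes the primary AUC0-72, is a change-from-baseline time point, and carries much of the weight in AUC0-120.

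**Working it through.** The plan gives no figure for this rule, so there is none to reproduce.

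**1. Weighting at 72 h (Visit 7 missed, 60 h and 120 h observed)**

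- The plain mean corresponds to (60 + 120)/2 = 90 h on a straight line.
- Interpolation weights: (120 - 72)/60 = 0.8 on V60 and (72 - 60)/60 = 0.2 on V120.
- Plain mean minus interpolation: (0.5 - 0.2) × (V120 - V60) = 0.3 × (V120 - V60).
- Trapezoid weight of the 72-h point: 12/2 = 6 h in AUC0-72, and (12 + 48)/2 = 30 h in AUC0-120.
- AUC differences: 0.3 × 6 = 1.8 h and 0.3 × 30 = 9 h, each times (V120 - V60).

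Before rounding, this favours both measures in an improving patient. Only rounding pulls them apart.

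**2. Rounding at 12 to 60 h (trapezoid weight 12 h)**

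Assumptions: rounding is to whole numbers and algometry is read to 0.1.

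- Means of two such readings lie on a 0.05 grid, so the loss averages 0.475 and is at most 0.95 N/cm².
- Per missed visit this is 0.475 × 12 = 5.7 (at most 0.95 × 12 = 11.4) N·h/cm².
- The mean loss exceeds 1% of AUC0-72 when a patient's average algometry is below 5.7/(72 × 0.01) = 7.9 N/cm².
- POM in whole mm: at most 0.5 × 12 = 6 mm·h. At a 30-mm average this is 6/(72 × 30) = 0.28%.

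**3. Both effects at a missed Visit 7**

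The documents give no time course. Assume V(t) = Vinf + (V0 - Vinf) × exp(-kt), and compare with the trapezoidal AUC from complete data. At k = 0.01/h:

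| Assumed course | True 72 h | Plain mean | Rounded down | Interpolated | AUC0-72 | Error: plain mean | Error: rounded (rule as written) | Error: interpolated |
|---|---|---|---|---|---|---|---|---|
| Algometry 1.25 to 2.5 | 1.892 | 1.969 | 1 | 1.876 | 115.77 | +0.40% | -4.62% | -0.08% |
| Algometry 5 to 12 | 8.593 | 9.025 | 9 | 8.505 | 504.30 | +0.51% | +0.48% | -0.10% |
| Algometry 10 to 25 | 17.699 | 18.625 | 18 | 17.511 | 1029.20 | +0.54% | +0.18% | -0.11% |
| POM 70 to 0 mm | 34.073 | 29.750 | 29 | 34.950 | 3597.04 | -0.72% | -0.85% | +0.15% |

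- First row: V60 = 1.814 and V120 = 2.124. The AUC0-72 error is 6 × (1 - 1.892)/115.77 = -4.62%. The AUC0-120 error is 30 × (1 - 1.892)/212.13 = -12.6%. The 72-h change from baseline becomes 1 - 1.25 = -0.25, against a true +0.64.
- At k = 0.005, 0.01, 0.02, 0.03 and 0.05/h, the net AUC0-72 error for the 5-to-12 and 10-to-25 courses runs from -0.67% to +0.48%. Rates in between can give slightly more.
- Before rounding, the plain mean overstates the 72-h change by 17.5%, 12.0%, 5.4%, 2.1% and 0.1% at those rates. Interpolation understates it by 1.3% to 2.9%.
- The absolute errors of plain mean and interpolation cross at k = 0.0279/h, a half-life of ln 2/0.0279 = 24.9 h. Above that rate the plain mean is closer.

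**4. Treatment contrast**

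Take 0.02/h against 0.01/h on the 10-to-25 course, with 20% missing Visit 7 in both arms. Before rounding, the AUC0-72 difference moves by 0.20 × 6 × (0.6146 - 0.9262)/195.75 = -0.19%; under interpolation it moves by -0.09%. At 5% missing the figures are -0.05% and -0.02%.

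**The case against.** **Little is at stake in the weighting.** On assumed curves the AUC0-72 contrast moves by at most 0.19%, and interpolation is not closer to the truth for every recovery rate. This stands. The argument for interpolation is consistency with the trapezoid and one convention for all visits, not proven accuracy.

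**The 60/120-h case is narrow.** A missed visit is to be rescheduled (Protocol 7.3), and visits are mapped to the nearest target time (SAP 14.2). If the make-up visit includes the measurements, a short delay still maps to Visit 7. One nearer 84 h maps to Visit 8, and the 60/84-h mean is then the linear 72-h value. Missing Visit 7 also means missing a site-applied dose. If that counts as a major violation, the patient leaves the primary PP set and the rule acts only in ITT/FAS. All this stands.

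**The blind review meeting can settle it.** Only partly. Its open mandate in SAP 14.8 is for issues the rules do not anticipate, and this rule is explicit.

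**Stronger readings to avoid.**

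- A reader might infer a biased treatment comparison. The documents give no missed-visit rate by arm, and with similar missingness much of the rounding effect cancels.
- A reader might quote the plain-mean errors as the effect of the rule. They are errors before rounding; at low algometry values rounding reverses their sign.
- A reader might take "Algometry will be performed at baseline and at each study visit" (Protocol 8.2.2), and "at baseline and at each subsequent study visit" for POM (Protocol 8.2.1), to mean that 84-h values exist. The schedule, visit lists and endpoint times say otherwise.
- A reader might call the SAP 14.8 bullet beginning "If a patient assesses spontaneous pain intensity and spontaneous pain relief at the time of rescue taken because of blunt trauma pain" a leftover to delete. Those two outcomes are not scheduled. But the bullet is the only definite rule for assessments within 6 h after rescue, and the SAP also lists a pain-at-rest VAS. It needs reconciling, not deletion.

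**Conclusion.** The point holds as a minor one. Rounding is the clearer defect: it acts in opposite directions on the two pain measures and serves no purpose for values that feed an AUC. It is material for an affected patient only at low algometry values: about -4.6% of AUC0-72 and -12.6% of AUC0-120 in the assumed 1.25-to-2.5 N/cm² case, which sits at the entry minimum. For the 5-to-25 N/cm² courses the net AUC0-72 error is within about 0.7% at the rates tried. The 72-h weighting is an inconsistency with a small AUC effect, and it reverses in merit above about 0.028/h.

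These sizes rest on whole-number rounding, the exponential curves and, for the per-visit rounding losses, algometry read to 0.1. The documents give no rounding precision, time course or missed-visit rate. No between-arm bias is shown.

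**What to change.** In SAP 14.8, impute a missed interior algometry or POM value by linear interpolation in time between the adjacent observed values, using the same time basis (nominal or actual) as the AUC, and without rounding. This matches SAP 5.4 and leaves imputation at 12 to 60 h as it is apart from the rounding. Keep rounding for ordinal scales only. The cost is a few lines of SAP text and code, with no new data. The SAP is finalised after the blind review meeting (SAP 1), so the change can be made before unblinding.

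Separately, reconcile these passages, which are not part of the imputation point:

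- the spontaneous-pain rescue bullet in SAP 14.8;
- the treatment-satisfaction assessment named there, since the trial's global assessments are efficacy and tolerability (Protocol 8.2.3);
- Protocol 8.2.1 and 8.2.2 with the schedule;
- the Visit 6 references in Protocol 4.4 (completion) and 6.8 (Day 11) with the 11-visit, 6-day schedule and with the PP definition, which requires completion.

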9.2 Sample Size Determination - Amended

This is a proof of concept study and therefore a specific statistical power calculation cannot be applied, however, assuming a comparable effect of the test gel vs. diclofenac – as suggested by pharmacological studies-, reference is made to similar studies (Predel, Br J Sports Med 2004;38:318–323), in which the standardized effect sizes of Algometry AUC 0-72 and POM VAS AUC 0-72 were over 1; with 30:15 patients, a drop-out rate of 10%, and a two-sided significance level $\alpha = 5\%$, a power $1 - \beta$ of about 80% is reached.

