14.2 Analysis populations

The following analysis populations will be used for analysis of study data:

Safety population: The safety population will include all randomized patients who received at least one dose of the IMP. Safety (e.g., AEs) will be analyzed in this population.

Intent to treat (ITT)/ Full Analysis Set (FAS): All subjects who are randomized and provide at least one measure of primary efficacy parameters after the first application of IMP.

Per protocol (PP) population: The Per Protocol population will include all subjects in ITT who complete the study and do not have any major protocol violations. Any exclusion from PP Population will be determined and documented prior to the database lock. The primary efficacy analysis population will be PP population and ITT/FAS Population will be secondary. The same analysis on ITT/FAS Population will be repeated for the primary and secondary and other efficacy endpoints to assess the robustness of the results based on PP Population.

Before the study is unblinded, each actual post-baseline visit will be mapped to the target visit time to which it is chronologically closest. The numbering of the actual visits (from Visit 1 to Visit 11) will then be changed as needed to improve the correspondence of the actual visit times to the protocol-specified schedule. Final determinations will also be made and documented before the study is unblinded to address visits that are equidistant to two nominal visit times or any other irregularities.

Before the study is unblinded, the timing of the diary assessments will be reviewed, and assessments will be reclassified into time slots as appropriate to ensure that all assessments in a given comparison were made a comparable amount of time after start of treatment.

	Trial Substance:	BAY H6689	Study No.:	21559
	Short Title:	Acute Soft Tissue of the Lower Extremities	Sponsor:	BAYER HEALTHCARE LLC.

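### Reason-dependent filling of visits after withdrawal can bias the ITT/FAS repeat, the only planned robustness check on the per-protocol primary result, in either direction

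*SAP*

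**What the plan says.** SAP 14.8 sets three rules for visits after premature termination:

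- Default: "all subsequent visits will be imputed by carrying the last non-missing observation forward".
- Suspected drug-related adverse event: "all subsequent visits will be imputed by carrying the baseline observation forward".
- Lack of efficacy: "all subsequent assessments will be imputed as the worst of all documented assessments".

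SAP 5.4 derives AUC by the trapezoidal rule, so every filled visit up to 72 h feeds the primary variable. Protocol 4.1.1.2 states that a higher algometry value means less pain, so a low early value carried forward counts as a poor outcome.

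SAP 14.4.1 makes the per-protocol set primary, and SAP 14.2 restricts that set to ITT subjects who complete the study without major violations. The same analysis is repeated on ITT/FAS "to assess the robustness of the results based on PP Population". No mixed model, multiple imputation or tipping-point analysis is planned. The treatment-by-center models in SAP 14.4.3 and 14.6 do not address missing data.

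**The concern.** Tenderness after an acute soft tissue injury should ease from visit to visit. The last-value rule assumes that recovery stops on the day the patient leaves. The baseline and worst-value rules go further and remove improvement already recorded. Which rule applies depends on the reason for leaving, and that reason can differ by arm. The single filled values are then analysed as if they had been observed.

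The per-protocol analysis leaves withdrawals out, so what ITT/FAS adds about them is largely set by these rules. If more placebo patients leave for lack of efficacy, worst-value filling lowers the placebo mean and favours naproxen. If more naproxen patients leave with suspected drug-related reactions, baseline filling works against naproxen. In both cases agreement or disagreement between the two populations could reflect the filling rule and not tenderness.

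**Working it through.** **1. The plan's own figure.** Protocol 9.2 gives "with 30:15 patients", "a drop-out rate of 10%, and a two-sided significance level" of 5%, and "standardized effect sizes of Algometry AUC 0-72 and POM VAS AUC 0-72 were over 1". After 10% loss, 30:15 becomes 27:13.5. With effect size 1 the noncentrality is 1/√(1/27 + 1/13.5) = 1/√0.1111 = 3.0. Power is Φ(3.0 − 1.96) = Φ(1.04) = 85.1% by the normal approximation and 83.3% by the noncentral t. The stated figure of about 80% is consistent and slightly conservative. The sample size is not at issue.

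**2. Effect on one patient (assumed recovery).** Suppose tenderness rises linearly from 2 to 8 N/cm² over 72 h and the last observation is at 24 h, with value 4.

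- True AUC0-72: (2 + 8)/2 × 72 = 360.
- Observed 0–24 h: (2 + 4)/2 × 24 = 72.
- Last value carried: 72 + 4 × 48 = 264, which is 27% low.
- Baseline or worst value (both 2): 72 + (4 + 2)/2 × 12 + 2 × 36 = 72 + 36 + 72 = 180, which is 50% low.

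**3. Effect on the test (simulation under equal true recovery).** None of these inputs except the arm sizes is in the documents: linear recovery with mean R = 2, 4 or 6 by 72 h, in units where the SD of the 72 h time-average given baseline is about 1 (intercept SD 0.7, slope SD 2, residual SD 0.4); withdrawal unrelated to outcome and after at least one post-baseline value; naproxen to placebo 30:15. The analysis is the SAP ANCOVA with baseline as covariate. Assumed withdrawal is 5% on naproxen and 20% on placebo: 0.05 × 30 + 0.20 × 15 = 1.5 + 3 = 4.5 of 45, which equals the planned 10% overall.

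| Rule | R = 2 | R = 4 | R = 6 |
|---|---|---|---|
| Worst value | 6.4% | 10.0% | 14.0% |
| Last value | 5.5% | 5.9% | 8.5% |

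These are two-sided false-positive rates at nominal 5%, from 3,000 trials per cell (Monte Carlo error about √(0.1 × 0.9/3000) = 0.5 points at a rate of 10%). A repeat over the same recoveries gave about 8–15% and 5–9%, so I quote roughly 6–15% and 5–9%. At the steep end the bias is about 0.30 SD (worst value) and 0.16 SD (last value), in favour of naproxen. Varying the patient-to-patient spread of recovery rates instead gave 11–18% and 6.5–9.6%, so the upper ends are not hard limits.

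**4. Other patterns, for R = 2 / 4 / 6, with all three arms (30:30:15).**

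- 10% withdrawal in every arm with the same reasons: 5.3 / 5.6 / 4.8%, bias about zero.
- Placebo 20%, mainly lack of efficacy, actives 7.5%: 5.8 / 7.5 / 10.6%.
- Placebo 30%, mainly lack of efficacy, actives 5%: 7.7 / 15.9 / 26.6%, nearly all favouring naproxen.
- Naproxen 7/30 with baseline carried forward, no other withdrawal: 6.5 / 11.9 / 18.8%, biased against naproxen.

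**5. A missing-at-random method.** In scenarios with R = 4 and unequal withdrawal, multiple imputation gave 3.9–5.8% with bias near zero, against 7.3–38.4% under the SAP rules; the 38.4% comes from an extreme case with 7/15 placebo withdrawals and none on the actives. Withdrawal was simulated as unrelated to outcome, which suits this method. Completers also stay near 5% there for the same reason.

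**The case against.** The inflation arises only if treatment changes withdrawal without changing tenderness recovery. If the gels do nothing in a blinded trial, withdrawal for lack of efficacy should not differ by arm, and the error rate stays near 5%. This stands, and it is why the point is conditional.

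More placebo withdrawal for lack of efficacy may itself be a treatment effect, and scoring it as failure is a defensible composite strategy. This also stands, but the SAP states no such estimand and presents the analysis as a robustness check.

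The documents make heavy withdrawal less likely. Patients who stop the gel stay under evaluation (Protocol 7.1), rescue is available without leaving (Protocol 4.2 and 6.10.1), and withdrawal is expected to be rare (Protocol 7.2, SAP 5.5). With few withdrawals the effect is small. Against that, three patients are already 20% of a placebo arm of 15.

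The trial is a proof of concept and ITT/FAS is secondary, which limits the consequence. The Blind Review Meeting may add handling rules (SAP 14.8), but it is not set up to replace these or to add a sensitivity analysis.

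A reader might infer that the primary test is inflated, or that the rules always favour naproxen. The documents support neither. The rules act mainly on the ITT/FAS repeat, and the baseline rule for drug-related events can work against naproxen. One qualification applies: Protocol 4.4 counts a participant as complete at Visit 6 (60 h), so a per-protocol subject could still lack the 72 h value.

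**Conclusion.** The point holds as a conditional weakness of the robustness check and should be addressed. The rules can bias the ITT/FAS comparison either way when withdrawal frequency or reason differs by arm. Under the assumed 5% versus 20% split, type I error is roughly 6–15% for the worst-value rule and 5–9% for the last-value rule; at moderate recovery the last-value rule is close to nominal.

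These sizes rest on an assumed recovery slope, SD and withdrawal split. The plan gives only "a drop-out rate of 10" percent overall, without arm or reason, so no single inflation figure can be read from the documents, and they do not show that inflation will occur. What they do show is that nothing planned would separate an effect of the filling rule from an effect on tenderness.

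**What to change.** In SAP 14.8 and 14.4.1, before unblinding, add for the ITT/FAS set a repeated-measures mixed model on the observed algometry values at 12, 24, 36, 48, 60 and 72 h:

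- Fixed effects: treatment by visit and baseline by visit, with no covariates beyond those of the primary model, so that ITT/FAS and per-protocol do not also differ in adjustment.
- REML, unstructured covariance (6 × 7/2 = 21 parameters) with a named fallback if it does not converge, and Kenward-Roger degrees of freedom because placebo has only 15 patients.
- Naproxen–placebo AUC0-72 difference as the trapezoid-weighted contrast of visit differences: 12 h weight for 12–60 h and 6 h for 72 h. The 6 h baseline weight drops out because the arms are compared at a common baseline.

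Report this beside the present rule-based ITT/FAS analysis. State that the rule-based analysis scores withdrawal for lack of efficacy or a drug-related adverse event as failure, while the mixed model assumes missing at random and estimates the difference had patients stayed. Tabulate withdrawals by arm, reason and last visit so that readers can judge which pattern applies.

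The cost is SAP wording, one extra model and a stated missing-at-random assumption that cannot be verified. No new data or visits are needed.
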